## Adverse Effects

The following summarizes the potential adverse effects in this study:

| Potential Adverse Effect | Description  |
|--------------------------|--|
| Severe Bruising          | The appearance of ecchymosis (purple colored spots or patches > 1cm); purpura (3-4 mm to 1cm); or petechiae (pin point red dots, < 3-4 mm) that is rated as severe by the investigator;    |
| Prolonged Bruising       | Bruising lasting longer than 1 month   |
| Severe Erythema          | The appearance of erythema (redness) that is rated as severe by the investigator   |
| Prolonged erythema       | Erythema lasting longer than 2 weeks.  |
| Severe Swelling          | The appearance of swelling (edema) that is rated as severe by the investigator   |
| Prolonged swelling       | Swelling lasting longer than 1 month. Prolonged swelling can lead to sensation of fullness in the back of the throat.  |
| First Degree Burn        | A first degree burn is superficial and causes local inflammation of the skin. The inflammation is characterized by pain, redness, and mild swelling. The skin may be very tender to touch. |
| Second Degree Burn       | Second degree burns are deeper and in addition to the pain, redness and inflammation, there is also blistering of the skin.  |

ZELTIQ P/N: [REDACTED]

Protocol Number: ZA17-004

This document and the contents hereof are considered proprietary and confidential information of ZELTIQ Aesthetics, Inc. Disclosure to unauthorized individuals or dissemination, publication or copying is prohibited without prior written consent of ZELTIQ.

|   |  |
|---|--|
| Third Degree Burn                                 | Third degree burns are deeper still, involving all layers of the skin. Because the nerves and blood vessels are damaged, third degree burns appear white, leathery and tend to be relatively painless. |
| Cold-induced panniculitis                         | Severe inflammation which requires medical or surgical intervention  |
| Skin Pigmentary Changes                           | The appearance of hyperpigmentation or hypopigmentation in the treatment area.   |
| Infection   | Infection at the treatment site, diagnosed by a physician and requiring medical intervention.  |
| Discomfort During Procedure                       | Discomfort reported during the procedure that is intolerable to the subject and results in an interruption or discontinuation of the procedure   |
| Discomfort Post Procedure                         | Significant discomfort, pain, cramping, tenderness, soreness, muscle spasm following the procedure which results in medical intervention (physician visit and/or prescription pain reliever)           |
| Prolonged Sensory Alteration Post Procedure       | Sensory changes (numbness, tingling, burning sensation) that are prolonged (i.e., lasting longer than 12 weeks).   |
| Sensory Alteration Requiring Medical Intervention | Sensory changes (pain, burning, stinging, hypersensitivity) with a severity warranting medical intervention.   |
| Vasovagal Symptoms                                | The occurrence of symptoms of anxiety, lightheadedness, dizziness, nausea, sweating, near syncope, or syncope (fainting).  |
| Motor nerve injury                                | Injury to the lower face motor nerves such as marginal mandibular nerve (lower lip weakness) or hypoglossal nerve (tongue deviation).  |
| Xerostomia  | Injury to the submandibular or parotid gland as evidenced by the subjective decrease in saliva production.   |
| Subcutaneous Induration                           | Generalized hardness and/or discrete nodules within the treatment area, which may develop after the treatment and may present with pain and/or discomfort.   |
| Paradoxical Hyperplasia                           | Visibly enlarged tissue volume within the treatment area that may develop within 2 - 5 months after treatment. Surgical intervention may be required.  |
| Contour Irregularity                              | Significant indentation or contour irregularity in the treatment area that would require surgical correction.  |
| Allergic/Irritant Contact Dermatitis              | Itchy rashes and skin peeling that may result from prolonged exposure to gel or applicator pressure  |
| Other   | Any other untoward medical event determined by the investigator to be an adverse event, regardless of the relationship to the device or treatment.   |

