a CoolMini or a [REDACTED] applicator) for fat layer reduction. In this study, subjects will receive up to 2 treatments at 6 weeks apart. [REDACTED]

[figure not shown]
[REDACTED] Subjects will be followed for 12 weeks after receiving final treatment. Follow-ups will be performed at the following time points: 1-week, 3-week, 6-weeks and 12-weeks post treatment. Final efficacy assessment will be performed at 12-weeks post 2nd treatment. **Figure 1** shows the overall study flow:

**Figure 1: Study Visit Flowchart.** All visits require subjects to return to the study site except for the 1-week and 3-week Follow-up phone/email.

[figure not shown]

\*Follow-up conducted remotely via phone call or email

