### **3.11. Study Photography**

Study candidates who sign the informed consent and meet eligibility criteria will be required to have baseline photographs of the intended treatment area taken. Baseline photographs will be taken using a standardized system prior to receiving the first treatment, and may also have additional photographs taken at subsequent treatment visits. All subjects will return 12 weeks after final treatment to have photographs of the treated area taken before exiting the study, using the same system and setup as baseline photographs.

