### **3.12.2. Treatment Visit #2; Optional: Week 6 post-Treatment #1 ( $\pm$ 1 week)**

Per the Investigator's discretion, subjects may receive a second treatment (up to 5 cooling cycles) after completion of the 6-week post-Treatment #1 follow-up evaluation.

1. All female subjects of childbearing potential will be asked to take a pregnancy test (urine) at the treatment visit. Exclude subject from participation if the results are positive.
2. Review and verify the subject continues to meet all eligibility criteria.
3. Obtain standardized photographs and 3-dimensional images (optional).
4. Measure fat layer thickness of the treatment area with a commercially-available ultrasound device using a standardized protocol (optional).
5. Perform treatment as described in Section 3.12.1., #6-9.

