## **3.13. Follow-up Procedures**

### **3.13.1. 1-Week Follow-Up Visit; Required: Day 7 ( $\pm$ 3 days)**

A phone contact will take place one week after each treatment visit to evaluate the condition of the treatment area, pain score, and adverse events. If there are any observations reported at the phone follow-up, the subject will be contacted by phone weekly until resolution of symptoms is documented. If there is evidence that an adverse event may have occurred, the subject will be asked to come in for a visit so an appropriate evaluation can be done. Email may be used as an alternate method of contact.

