### **3.13.4. 12-Week Final Follow-Up Evaluation; Required (12 weeks $\pm$ 14 days post final treatment)**

The following evaluations will be performed at the 12-week follow-up visit after the final treatment visit:

1. Obtain weight.
2. Obtain photographs using standardized setup and settings. In addition, 3-dimensional images may be captured.
3. Measure fat layer thickness of the treatment area with a commercially-available ultrasound device using a standardized protocol.
4. Perform clinical assessment of the treatment areas for any epidermal, dermal and subcutaneous findings (e.g., erythema, bruising, swelling, pigment changes).
5. Assess for alterations in sensation (e.g., numbness, tingling). Assess subject pain score using 0 – 10 scale.
6. Examine the oral cavity for evidence of dry mouth.
7. Assess lower face motor nerve function.
8. Assess for any adverse events.

9. Administer subject questionnaire to obtain subject feedback on overall satisfaction.

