## Anticipated Device Effects

These are known effects of the ZELTIQ Procedure, previously recorded in prior studies as transient and/or temporary effects related to the cold application and/or vacuum pressure inherent in the treatment. Anticipated effects of the device which will not be considered adverse events include:

- inflammation of the subcutaneous fat layer, which is a desired effect of the procedure;
- sensations of coldness, stinging, burning, pinching, or pressure associated with placement of the applicator and the initiation of the cold treatment;
- known skin effects (e.g., blanching; erythema, bruising, purpura, petechiae, swelling, discomfort, tenderness, or soreness at the treatment site, all mild to moderate in nature) which are temporary effects that resolve spontaneously shortly after the procedure;
- localized sensory changes (e.g., numbness, tingling) at the treatment area resolving within 12 weeks of the procedure;

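### Prolonged sensory alteration may be under-ascertained: the final visit can fall on or before the 12-week threshold that defines the event, and the start of the count is undefined when two treatments are given

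*Combined protocol and SAP*

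**What the plan says.** Section 7.2 sorts sensory change by how long it lasts.

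- Under Anticipated Device Effects, the effects that are not adverse events include "localized sensory changes (e.g., numbness, tingling) at the treatment area resolving within 12 weeks of the procedure".
- Under Adverse Effects, Prolonged Sensory Alteration is defined as "Sensory changes (numbness, tingling, burning sensation) that are prolonged (i.e., lasting longer than 12 weeks".

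Follow-up ends at about the same time.

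- Section 2.1: "Subjects will be followed for 12 weeks after receiving final treatment".
- Section 3.13.4 sets the last visit at 12 weeks with a tolerance of ± "14 days post final treatment". Sensation and adverse events are both assessed there.
- Section 3.11: "All subjects will return 12 weeks after final treatment to have photographs of the treated area taken before exiting the study".

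Section 3.13.1 has a rule for continuing contact: "If there are any observations reported at the phone follow-up, the subject will be contacted by phone weekly until resolution of symptoms is documented". Section 3.13.2 repeats it for the 3-week contact. Sections 3.13.3 and 3.13.4, which cover the in-person 6-week and 12-week visits, have no such rule.

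A second treatment is optional. By section 3.12.2, "subjects may receive a second treatment (up to 5 cooling cycles) after completion of the 6-week post-Treatment #1 follow-up evaluation", at week 6 ± 1 week.

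**The concern.** The event is defined by passing 12 weeks, and the last scheduled look is at 12 weeks, give or take two. A subject who is still numb at an on-time or early final visit fits neither list: the change has not resolved within 12 weeks, and it has not yet lasted longer. The plan does not say how to classify that subject or whether anyone calls again.

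The second difficulty is the starting point. The anticipated-effects list counts from a single procedure, although a subject may have two. The adverse-effects list counts duration. Two sites could code the same history differently.

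Section 3.14.1 makes the rate of device- or procedure-related adverse events the primary safety endpoint, and section 3.16.3 tabulates subjects by type of adverse event. A sensory change never labelled an adverse event drops out of both. With at most 45 subjects and no control group, a few cases either way change the reported rate.

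**Working it through.** The plan gives no rate or calculation on this point to reproduce, so the check is date arithmetic on its windows.

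**Inputs**
- Threshold: 12 × 7 = 84 days; the event needs a duration above 84 (section 7.2).
- Final visit: 84 ± 14 = day 70 to 98 after the final treatment (section 3.13.4, Table 2).
- 3-week contact: 21 ± 7 = day 14 to 28 after each treatment (section 3.13.2, Table 2).
- Treatment #2: 42 ± 7 = day 35 to 49 after Treatment #1 (section 3.12.2).
- Sample size: at most 45 (section 3.6).
- True rate of sensory change beyond 84 days: not given. I assume 2%, 5% and 10% for illustration only.

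**1. Can the final visit confirm the event?** Permitted days: 98 − 70 + 1 = 29. Days at or before the threshold: 84 − 70 + 1 = 15. For a change that began on the day of the final treatment, 15/29 = 51.7% of permitted days, including the nominal day 84, are too early to show more than 84 days. The other 14/29 = 48.3% are late enough.

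**2. Which changes does the call rule reach?** To exceed 84 days by the latest permitted visit, a change must begin before day 98 − 84 = 14. The 3-week contact is never earlier than day 14, so any such continuous change is already present at that contact. If the subject reports it, weekly calls start. A change that begins after the 3-week contact is not reached by the rule and cannot pass 84 days at any permitted final visit.

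**3. Two treatments.** Counted from Treatment #1, the final visit falls between 35 + 70 = 105 and 49 + 98 = 147 days (nominal 42 + 84 = 126). A change continuous since Treatment #1 is therefore past 84 days by then if its whole duration is counted. If the 12 weeks run from the latest treatment, a change resolving by day 35 + 84 = 119 to 49 + 84 = 133 still counts as resolved in time. Example: onset at Treatment #1, Treatment #2 on day 42, resolution on day 120. The duration is 120 days, an adverse event under one list. Resolution came 120 − 42 = 78 days after the latest treatment, an anticipated effect under the other list if it is read that way.

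**4. Illustration, not an estimate.** Assume 45 subjects, final visits uniform over the 29 days, onset at the final treatment, and no weekly calls. The recorded rate is p × 14/29, and the chance of at least one case is 1 − (1 − rate)^45.

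| True rate p | Recorded rate | P(≥1 case), all found | P(≥1 case), final visit only |
|---|---|---|---|
| 2% | 1.0% | 60% | 35% |
| 5% | 2.4% | 90% | 67% |
| 10% | 4.8% | 99% | 89% |

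**The case against.** The best answer is the weekly-call rule. By step 2, every continuous change that could pass 84 days by the last permitted visit is present at the 3-week contact, and reporting it there triggers calls with no stated end date. The 3-week contact was added, according to the summary of changes, to monitor ongoing side effects and observations, so numbness plausibly qualifies. Section 3.13.5 also allows up to four optional evaluations, section 3.2 allows up to six months per subject, and the Other row of the adverse-effects table lets the investigator record any untoward event. Section 3.11 is about photography; it does not say that calls already running must stop.

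Much of this stands. A reader might infer that prolonged numbness will certainly be missed whenever the final visit is early. The documents do not support that: if the rule is followed and kept up after exit, a change reported at week 1 or 3 is tracked past day 84. What remains is that the rule depends on a telephone or email report, is absent from the visits where sensation is examined in person, and is not said to outlast the 12-week follow-up. The optional visits and the Other row are discretionary.

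A reader might also infer that Treatment #2 restarts the clock, so that twice-treated subjects are under-counted most. No section states a restart. Counted by duration, those subjects are observed for longer, 105 to 147 days from Treatment #1. The restart is only one reading of undefined wording.

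**Conclusion.** The point holds as a risk of under-ascertainment. For a change dating from the final treatment, an on-time or early final visit cannot itself confirm the event, and the plan neither follows nor classifies a change still present at exit. With two treatments, the two lists in section 7.2 leave a change lasting up to 119 to 133 days from Treatment #1 open to either class.

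The 15 of 29 is a share of calendar days, not of subjects or cases. The documents give no distribution of visit days, no rate of persistent sensory change, and no statement on whether calls continue after exit, so neither the size of an under-count nor its existence can be derived. The table in the working shows what would follow only if the calls contributed nothing. This is a worthwhile, inexpensive improvement to a descriptive safety analysis, not a flaw that invalidates it.

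**What to change.** - **Section 3.13.4:** extend the existing weekly-contact rule to any sensory change present at the 12-week visit, until it resolves or its duration passes the protocol's own 12-week threshold. State that these contacts continue after the visit.
- **Section 3.16.3:** tabulate sensory changes unresolved at last contact as ongoing, in their own row, rather than leaving them out as non-events.
- **Section 7.2:** reconcile the anticipated-effects and adverse-effects entries so that one stated starting point applies when there are two treatments. Which one is for the sponsor and the investigators to decide; the statistical need is that it is the same in both lists and fixed before the data are coded.

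Cost: for a change dating from the final treatment in a subject seen on day 70, about three weekly calls (days 77, 84 and 91, the last being the first beyond 84). A change that first appears near the final visit could need up to about 12 weeks of calls. The reported adverse event rate may rise. Treatment is unaffected.
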